5. ANALYSIS OF STUDY OUTCOME MEASURES DESCRIBING PLATELET USE

5.1 Platelet transfusion day prevalence rates

The prevalence rate is the rate of events (new and recurring events) over a specified time period. The platelet transfusion day prevalence rate in a certain time period is defined as the number of platelet transfusion days per 100 NICU admission days in this period. A platelet transfusion day is defined as any day after birth on which the infant received at least one platelet transfusion.

$$\textit{Prevalence rate} = \frac{\textit{Number of RBC transfusions days during study period}}{\textit{Number of admission days in follow up during study period}} \times 100 \ \textit{days}$$

The platelet transfusion day prevalence rate is calculated in each center and pooled per country. We expect a large between country variability, therefore all prevalence rates are pooled using random effects Poisson models described by Stijnen et al. (2010). This model uses the exact within-study likelihood instead of the approximate normal within-study likelihood which is known to perform better with low event rates and small sample sizes. Additionally, this method does not require the use of an continuity correction in case centers have a prevalence rate of 0 platelet transfusion days. (2) Pooling is done using the function "metarate" of the R-package Meta.

Subgroup rates and overall rate will be presented with 95% confidence intervals in a forest plot. Prevalence rates will only presented on country level.

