5.2.1. Average expected platelet transfusion day prevalence rate per country

A logistic regression model is used to estimate the probability that a NICU admission day is a platelet transfusion day based on several covariables, for each individual admission day in study follow-up. To account for the repeated measures within an infant, the model is fitted using generalized estimation equations (GEE).

Probabilities are calculated individually for each patient for each NICU admission day in study follow-up and summarized per country to calculate the average predicted platelet transfusion day prevalence rate.

Average expected RBC transfusion day prevalence rate per country =

Sum of predicted probability per admission day over admission days over infants per country

Number of admission days per country

The following variables are included in the regression analyses. The clinical variables could vary over time and are included under the assumption that experiencing these events leads to an increased risk of transfusion and not vice versa.

- Baseline variables: sex, gestational age at birth, birth weight, congenital anomalies, intrauterine growth restriction (birth weight below 10th percentile) (3)
- Clinical variables: major bleeding, NEC, sepsis, mechanical ventilation, surgical procedure, postnatal day

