5.2.2. Observed / expected prevalence rate ratio per country

The prevalence rate ratio per country is defined as the country's observed platelet transfusion day prevalence (as calculated in section 5.1) compared to the country's average expected platelet transfusion day prevalence rate.

Prevalence rate ratio per country =

Observed platelet day prevalence rate per country

Average expected platelet day prevalence rate per country

Observed / expected prevalence rate ratios will be presented in an observed/expected funnel plot.

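### The O/E funnel plot sets a random-effects pooled rate over a crude day-average and has no stated limits, so the ratio is not centred at 1 when centres vary and plain expected-count limits would not fit it

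*SAP*

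**What the plan says.** The case-mix adjusted platelet transfusion day rate is the second of three main outcomes (SAP 2.1). Section 5.2 builds it so that countries can be compared fairly.

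- **Numerator (5.2.2).** The ratio is "defined as the country's observed platelet transfusion day prevalence (as calculated in section 5.1", divided by the expected rate. Section 5.1 says that "The platelet transfusion day prevalence rate is calculated in each center and pooled per country" and that "all prevalence rates are pooled using random effects Poisson models".
- **Denominator (5.2.1).** The expected rate is "Sum of predicted probability per admission day over admission days over infants per country", divided by the country's number of admission days. This is a crude day-weighted mean.
- **Clustering (5.2.1).** "To account for the repeated measures within an infant, the model is fitted using generalized estimation equations (GEE". Dependence is mentioned nowhere else in section 5.2.
- **Display (5.2.2).** "Observed / expected prevalence rate ratios will be presented in an observed/expected funnel plot". Nothing more is said about the plot.
- **Adjusted rate (5.2.3).** The same ratio is multiplied by the overall unadjusted rate.

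Sections 5.1 and 5.3 plan 95% confidence intervals for the other two main outcomes. Sections 5.2.1 to 5.2.3 plan none for the ratio or the adjusted rate.

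**The concern.** A funnel plot is read by its centre line and its limits. The usual O/E funnel is centred at 1 and takes its limits from the expected count, which assumes that the numerator is a Poisson count with that expectation. The ratio in 5.2.2 departs from this in two ways.

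1. The numerator and denominator average over centres differently. A random-effects Poisson model with normal effects on the log scale estimates the rate of a typical (median) centre. The denominator reflects the day-weighted mean. When centres differ, the first lies below the second.
2. Transfusion days recur in the same infants and may cluster by centre, so observed days vary more than a Poisson count. Using GEE to fit the prediction model does not supply the variance of O/E.

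The funnel plot is the only planned display of how far a country's case-mix adjusted result departs from 1 relative to chance. If its centre and limits do not suit the ratio, countries with average practice can look different. If the limits are left open, they may be chosen after the country results are known.

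**Working it through.** The SAP states no event count, number of infants or centres per country, limit level or clustering measure, so there is no figure of its own to reproduce. All numerical inputs below are assumptions.

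**Step 1: centre of the ratio.** Let centre rates be r × exp(u), with u normal, SD τ and mean −τ²/2, so that the mean rate is r in every country. The crude expected rate is r. The random-effects pooled rate targets exp(mean log rate) = r × exp(−τ²/2). The ratio under identical practice is therefore centred near exp(−τ²/2):

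| Centre log-rate SD τ | exp(−τ²/2) |
|---|---|
| 0 | 1.00 |
| 0.3 | exp(−0.045) = 0.96 |
| 0.5 | exp(−0.125) = 0.88 |
| 0.8 | exp(−0.32) = 0.73 |

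A simulation that fitted the random-effects model (3, 6 or 10 centres, 1.2 transfusion days per 100 days, 300 runs per setting, no infant clustering) gave median O/E of 0.86 to 0.88 at τ = 0.5 and 0.69 to 0.72 at τ = 0.8. This agrees in direction and roughly in size. A country with a single centre has nothing to pool, so its pooled and crude rates coincide and this source of shift does not arise. The shift would then differ between countries.

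**Step 2: width of the limits.** Suppose the crude ratio is used and is centred at 1, with variance φ/E, where E is expected transfusion days and φ the variance inflation. Limits 1 ± z/√E then flag a share 2 × (1 − Φ(z/√φ)) of countries with identical practice:

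| φ | 95% limits (z = 1.96) | 99.8% limits (z = 3.09) |
|---|---|---|
| 1 | 5.0% | 0.2% |
| 2 | 16.6% | 2.9% |
| 3 | 25.8% | 7.4% |
| 4 | 32.7% | 12.2% |

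To give φ a meaning: if transfused infants arrive as a Poisson count and days per transfused infant are geometric with mean m, then φ = E[X²]/E[X] = (2m² − m)/m = 2m − 1. So φ = 2, 3 or 4 corresponds to m = 1.5, 2 or 2.5 days, before any reduction through the case-mix covariates.

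**Step 3: how far this depends on the assumptions.** Countries with identical mean practice were simulated with 1, 3 or 6 centres of 30 infants, about 20 days each (capped at 42), 0.5 to 2 transfusion days per 100 days, and exact Poisson 95% limits on the crude count. About 2 to 5% were flagged without clustering. With infant clustering the share ran from about 4% (rare events, mild clustering) to 53% (2 per 100 days, strong infant and centre clustering). A middle case (3 or 6 centres, 1 per 100 days, strong infant clustering, no centre effect) gave 26%, and 8 to 9% at 99.8% limits. With the random-effects numerator, 95% limits flagged about 3 to 7% without clustering, 12 to 14% at τ = 0.3 and 20 to 33% at τ = 0.5.

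**Step 4: after the change.** Limits 1 ± z × √(φ/E) around a crude ratio return the nominal 5% or 0.2% by construction; a compound-Poisson simulation gave 4 to 5% at the 95% level. For scale, with E = 30 and φ = 3 (both assumed), plain 95% limits are 1 ± 1.96/√30 = 0.64 to 1.36, and scaled limits are 1 ± 1.96 × √(3/30) = 0.38 to 1.62.

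**The case against.** **The SAP is silent on limits rather than wrong.** It names no Poisson limits, no level and no outlier rule. This stands. A reader might infer that the plan will flag a quarter to a third of countries falsely. The document does not support that: the figure needs 95% limits and φ of about 3 to 4 (2.9 to 4.1), and the SAP gives neither.

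**φ may be smaller than the illustrations.** The prediction model uses daily status for bleeding, NEC, sepsis, ventilation and surgery, plus postnatal day. Runs of transfusions during such episodes are partly carried into the expected rate, and only residual inflation counts. Each country's own days also enter the model, which pulls O/E somewhat towards 1. Both stand and limit what can be said about size. They give no reason to expect that residual clustering vanishes.

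**Funnel limits do not enter the adjusted rate.** Correct. A reader might infer that false signals in the plot would become the study's conclusion on main outcome 2. The SAP does not say so: the adjusted rate in 5.2.3 is computed without the limits, and no section plans to label countries as over- or under-users. The numerator, however, does pass into 5.2.3.

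**The displayed formula in 5.1 is a crude ratio.** If 5.2.2 meant that formula, the shift in Step 1 would disappear. But the text of 5.1 says that country rates are obtained by pooling centre rates, and 5.2.2 points to the rate as calculated there. At the least the SAP must say which is meant, and the need for stated, clustering-aware limits remains under either reading.

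**Conclusion.** The point holds in this form. As written, the ratio in 5.2.2 is not observed days over their expectation, and the funnel plot that displays it has no stated limits. With between-centre variation the ratio centres below 1 under identical practice: about 0.88 at an assumed log-rate SD of 0.5, and nearer 1 if centres vary less. The SAP says "We expect a large between country variability" but gives no size for variation between centres, so the true shift is unknown. Expected-count limits, if used, would be too narrow whenever residual φ exceeds 1. The illustrative false-flag shares are 17%, 26% or 33% at 95% limits and 3%, 7% or 12% at 99.8% limits for φ = 2, 3 or 4. These are conditional on assumed inputs and do not predict this study's results. The direction of both effects follows from the stated method; their size does not.

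**What to change.** In section 5.2.2:

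1. Define O/E per country as crude observed platelet transfusion days divided by the sum of predicted probabilities over the country's admission days. Replace the reference to the pooled 5.1 rate, and state that section 5.2.3 uses this same ratio, so that the plotted and the adjusted figures agree. The pooled rates can stay in the 5.1 forest plot.
2. Plot O/E against expected transfusion days, with the centre line at 1, and state the limit level.
3. Draw limits that allow for clustering, for example 1 ± z × √(φ/E), with φ estimated from infant-level sums as Σ(Oᵢ − Eᵢ)²/ΣEᵢ, or limits from resampling whole infants within centres.
4. Say which source of variation the limits cover. Infant-level limits leave practice differences between centres as part of the signal, whereas centre-level sums would absorb them. The two are not interchangeable.

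The cost is a few sentences in the SAP and a few lines of code on data already held. The downside is wider limits, so fewer countries will stand out.

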5.2.3 Case-mix adjusted prevalence rates

The standardized platelet transfusion day prevalence rates are defined as the prevalence rate ratio for a country multiplied with the overall unadjusted platelet prevalence rate.

 $\label{eq:case-mix} \textit{Case-mix adjusted prevalence rate per country} = \\ \textit{Prevalence rate ratio per country} * \textit{overall unadjusted platelet prevalence rate} \\$

5.3 Cumulative incidence of receiving at least one platelet transfusion

The cumulative incidence (with 95% confidence interval) of receiving at least one platelet transfusion during the first 28 days of life will be calculated where death and discharge are considered as competing events. Infants that were already present at the NICU at the start of the study period are excluded, because the first platelet transfusion for these infants could have happened before the study period. Event time for infants who were transferred or discharged during the first 28 days of life were censored. The cumulative incidence was calculated in R with the package "cmprsk" using function "cuminc".

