1. STUDY SUMMARY

Study rationale: Premature infants are a highly transfused group, though robust evidence supporting neonatal transfusion practice is scarce. The PlaNeT-2/MATISSE platelet transfusion trial found that a 25×10^9 /L platelet count threshold was superior to a 50×10^9 /L threshold in preterm infants, with higher mortality and major bleeding rates in the latter liberal threshold group. (1) There are no neonatal transfusion guidelines that have been implemented by Europe as a whole, resulting in significant variation in transfusion practice within Europe. Detailed contemporary data on neonatal transfusion practices in Europe, including the use of platelet transfusions, are lacking.

Study population: preterm infants born below 32 weeks gestation admitted to a tertiary level Neonatal Intensive Care Unit (NICU)

Study design: prospective, international, multicenter, observational study

Study data collection: data collection took place from September 2022 to August 2023. All participating centers collected data during a fixed six-week study period. Local sites documented transfusion use in all infants in their NICU during these weeks, including infants already admitted at the start of the study period or newly admitted during the study period. Consequently, not all infants were followed from birth, and the duration of study follow-up varied, with a maximum follow-up of 42 days per included patient.

 ${\it Infographic was made using images of Juicy_Fish from FlatIcon}.$

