4.4 Patient and center characteristics

The following descriptive data on patient and center characteristics will be presented.

Patient characteristics (for total and per country)

- Number of patient included
- Total number of admission days in study follow-up
- Duration of study follow-up per patient, in days
- Postnatal age at start follow-up in the study, in days
- Sex, % female
- Gestational age at birth, in days
- Birth weight, in grams
- Multifetal pregnancy, % singleton
- Patients with congenital anomalies, %
- Patients with intrauterine growth restriction, %
- Patients with at least one major bleeding during study follow-up, %
- Patients with at least one NEC episode during study follow-up, %
- Patients with at least one sepsis episode during study follow-up, %
- Patients with at least one day of mechanical ventilation during study follow-up, %
- Patients with at least one surgical procedure during study follow-up, %

Participating centers (for total and per country)

- Number of academic centers, %
- Number of centers that perform NEC surgery, %
- Number of larger centers (caring >100 preterm infants with a GA below 32 weeks yearly on average), %

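### Section 5.3 excludes infants already in the NICU because an earlier transfusion could be unseen, but keeps infants first admitted days after birth, to whom the same reason applies

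*SAP*

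**What the plan says.** The study enrols by presence in, or admission to, a tertiary NICU below 32 weeks' gestation, not by birth in the centre. SAP section 1 covers every infant in the unit during the six weeks, "including infants already admitted at the start of the study period or newly admitted during the study period", with no limit on postnatal age at admission. It adds that "not all infants were followed from birth, and the duration of study follow-up varied".

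Section 5.3 defines the third main outcome on the age scale: "receiving at least one platelet transfusion during the first 28 days of life", with death and discharge as competing events. One group is left out: "Infants that were already present at the NICU at the start of the study period are excluded", and the reason given is "because the first platelet transfusion for these infants could have happened before the study period". For movements between hospitals the section has one rule: "Event time for infants who were transferred or discharged during the first 28 days of life were censored". The estimator is `cuminc` from the R package `cmprsk`. No entry time or delayed-entry method is named.

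Section 4.4 lists "Postnatal age at start follow-up in the study, in days" among the patient characteristics to be reported, so age at entry is available.

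**The concern.** The exclusion depends on whether the infant was in the unit on the calendar day the study opened. Its rationale is whether the infant was observed from birth. The two agree for an infant admitted on the day of birth, but not for one who is first admitted during the six weeks some days after birth. That infant was not present at study start and so stays in the analysis, yet a first transfusion may have been given elsewhere before follow-up began.

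Two errors follow. First, the infant sits in the risk set from birth to admission, a period in which no event could be recorded; this is delayed entry treated as event-free time. Second, if the infant was transfused before admission, that event is lost, or a later transfusion is recorded as the first. Both affect one of the three main outcomes in section 2.1.

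**Working it through.** The SAP gives no rate, sample size or count of late entrants for this outcome, so there is no figure of its own to reproduce. The check has two parts.

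**Reading the rules together.** Take an infant born elsewhere and first admitted to a participating NICU on day 8 of life, during week 2 of that centre's study period.

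1. Enrolled under section 1? Yes, as a newly admitted infant.
2. Removed by the exclusion in 5.3? No; the infant was not present when the period began.
3. Covered by the transfer rule in 5.3? No; that rule censors infants who leave and says nothing about infants who arrive late.
4. Handled by the estimator? No; `cuminc` takes one follow-up time and one status per infant. On the days-of-life scale, days 1 to 7 count as time at risk without an event.

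**Size, under assumptions only.** Let *F* be the true 28-day risk, *q* the share of the analysis set who enter late, *g* the share of their first transfusions that fall before entry, and *r* the probability that an infant transfused before entry is transfused again and counted as a first event. With equal underlying risk and no competing events or censoring:

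estimate = (1 − q)F + qF[(1 − g) + g·r], so relative error = −q·g·(1 − r).

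Assumed inputs (none is in the SAP): a transfusion probability of 1% per day in days 1–7 and 0.2% per day afterwards; entry at the start of a day uniform over days 3–20.

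- F = 1 − 0.99^7 × 0.998^21 = 1 − 0.9321 × 0.9588 = 10.6%.
- Average risk already passed at entry (2 to 19 completed days) is about 6.8%, so g = 6.8/10.6 ≈ 0.64.

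| Late entrants q | Estimate, r = 0 | Relative error, r = 0 | Relative error, r = 0.5 |
|---|---|---|---|
| 0% | 10.6% | 0% | 0% |
| 5% | 10.3% | −3.2% | −1.6% |
| 10% | 9.95% | −6.4% | −3.2% |
| 20% | 9.3% | −12.8% | −6.4% |
| 30% | 8.6% | −19.2% | −9.6% |

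A wider set of assumptions (q 5–30%, g 0.3–0.6, r 0–0.5) gives a relative understatement from 0.05 × 0.3 × 0.5 = 0.75% to 0.30 × 0.6 × 1 = 18%.

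**Direction.** Suppose late entrants have twice the risk, with F = 10% in the others, q = 15%, g = 0.6 and r = 0.5. The estimate is 0.85 × 10% + 0.15 × 20% × (0.4 + 0.3) = 8.5% + 2.1% = 10.6%. That is above the 10% in infants followed from birth but below the 11.5% (8.5% + 3.0%) true for the whole mixed group. Whether the result reads too high or too low therefore depends on the risk of the late entrants and on the population it is meant to describe.

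**The case against.** The SAP never mentions infants transferred in. It keeps them by omission, not by a stated decision, and it does not say how many there were or whether transfusions before admission were recorded. The sentence in section 1 about follow-up not starting at birth can be read as referring to infants already admitted, the group that 5.3 removes. Eligibility detail and the content of the case report form may sit in a protocol that is not shown. All of this stands as a limit on size. It does not remove the point: section 5.3 fixes an analysis set that, as worded, does not meet its own reason for exclusion.

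Three stronger readings are tempting, and the document does not support them.

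- *That comparisons between countries are distorted.* Section 5.3 plans a cumulative incidence without mentioning country. Country-level results are planned for the prevalence rates in sections 5.1 and 5.2 and for the descriptive tables in 4.4.
- *That the bias is known to be substantial and downward.* The upper figures above need many late entrants, most of their first transfusions before entry, and no repeat transfusion counted as a first event. The range starts at zero, and the direction is not fixed.
- *That late entrants certainly have an unknown history.* The SAP shows only that their earlier transfusions are not described. The reason given for excluding infants already present suggests that such history was not to hand, but does not prove it.

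**Conclusion.** The point holds as a mismatch between the exclusion rule in 5.3 and its stated reason. Wherever infants are first admitted after the day of birth, following the rule as written puts unobserved days into the risk set of a main outcome and can miss or misdate first transfusions. The size cannot be determined from the SAP. The illustrative 0% to 19% rests wholly on the assumed daily risks, the spread of entry days, equal underlying risk, no competing events and pre-entry events never being counted. If no infant entered late, the effect is nil and a sentence saying so would settle the matter. The prevalence rates in 5.1 and 5.2 count admission days in follow-up and are not touched by this point.

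**What to change.** In section 5.3, replace the exclusion based on presence at study start with one based on age at entry: include only infants whose study follow-up starts on postnatal day 1, allowing day 2 for same-night transfers, using the postnatal age at start of follow-up listed in 4.4. Report how many newly admitted infants this removes, and state that the estimate describes infants followed from about birth.

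An Aalen-Johansen estimator with delayed entry is an alternative only if transfusion status before admission was recorded, and then only for infants known to be untransfused at entry. Delayed entry alone does not resolve an unknown earlier transfusion.

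The cost is one clause and one filter on an existing variable, the loss of some infants from this analysis, and a narrower target than all infants admitted to a tertiary NICU.

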2.1 Main study outcome measures

- 1. Platelet transfusion day prevalence rate
- 2. Case-mix adjusted platelet transfusion day rate
- 3. Cumulative incidence of receiving at least one platelet transfusion during first 28 days of life

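### SAP section 5.3 codes discharge both as a competing event and as censored for main outcome 3; following the censoring sentence would overstate the 28-day cumulative incidence

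*SAP*

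**What the plan says.** SAP section 2.1 lists as its third main outcome: "Cumulative incidence of receiving at least one platelet transfusion during first 28 days of life". Section 5.3 is the only place where its analysis is described. Four elements matter here.

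- First sentence: the cumulative incidence is calculated "where death and discharge are considered as competing events".
- Second sentence: "Infants that were already present at the NICU at the start of the study period are excluded", so the analysis set is infants newly admitted during the study period.
- Third sentence: "Event time for infants who were transferred or discharged during the first 28 days of life were censored".
- Last sentence: the estimator is `cuminc` from the R package `cmprsk`.

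Section 1 adds that "the duration of study follow-up varied, with a maximum follow-up of 42 days per included patient". Some infants will therefore reach the end of the six-week window before day 28 of life. No section distinguishes discharge from transfer, or says whether the target is transfusion in the study NICU or in any hospital.

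**The concern.** In a competing-risks analysis, a competing event and a censoring are opposite statements about what happens next. Coding discharge as a competing event says that the infant has left the setting and will not contribute a first transfusion. Coding it as censored says that the infant remains at risk, unobserved, at the same rate as infants still in the NICU. The same infant cannot carry both codes.

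Two analysts working from section 5.3 could therefore report different values for a main outcome, each with a sentence of the SAP in support. The one who censors discharge estimates something closer to the risk if no infant were ever discharged, not the proportion who receive a platelet transfusion when discharge competes.

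**Working it through.** **Step 1: the two codings side by side.**

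| Exit from follow-up | 5.3, first sentence | 5.3, third sentence |
|---|---|---|
| Death | competing | not mentioned |
| Discharge | competing | censored |
| Transfer | not mentioned | censored |

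Only the discharge row conflicts.

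**Step 2: direction for discharge.** Let a, b and c be the daily hazards of first transfusion, death and discharge. With constant hazards over 28 days:

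- discharge competing: F = a/(a+b+c) × [1 − (1−a−b−c)^28]
- discharge censored: F = a/(a+b) × [1 − (1−a−b)^28]

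Each day adds a × (proportion still at risk). Censoring drops c from the depletion of that proportion, so it is never smaller and is larger once any discharge has occurred. For any a > 0 and c > 0 the censored value is higher. The same argument holds when the hazards vary by day.

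**Step 3: size for discharge.** The SAP gives no rates, so there is no figure of its own to reproduce and every input here is assumed. Hazards were set so that, with discharge competing, 28-day transfusion is 5%, 10% or 15%, death 7%, and discharge 10% to 60%.

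Worked case: flat hazards, transfusion 10%, discharge 50%. This needs a = 0.00579, b = 0.00406, c = 0.02897.

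- Competing: 0.00579/0.03882 × (1 − 0.96118^28) = 0.149 × 0.670 = 10.0%
- Censored: 0.00579/0.00985 × (1 − 0.99015^28) = 0.588 × 0.242 = 14.2%
- Ratio: 1.42

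Censored value when the competing-event value is 10%:

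| Discharged by day 28 | Flat hazards | Early transfusion, late discharge |
|---|---|---|
| 10% | 10.6% | 10.1% |
| 30% | 12.0% | 10.5% |
| 50% | 14.2% | 10.9% |
| 60% | 16.0% | 11.3% |

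In the right-hand column the transfusion hazard decays as exp(−day/7), the death hazard decays as exp(−day/10), and the discharge hazard in week 1 is one fifth of its later level. Across all transfusion levels and both shapes the ratio of censored to competing runs from 1.01 to 1.65.

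**Step 4: transfer.** Suppose the target is transfusion in any hospital, and the transfusion hazard after transfer is k times the hazard before it. With assumed daily hazards of 0.005 (transfusion), 0.003 (death) and 0.02 (transfer), censoring at transfer gives 0.005/0.008 × (1 − 0.992^28) = 12.6%.

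| k | True 28-day risk | Bias from censoring transfer |
|---|---|---|
| 0 | 9.8% | upward |
| 0.5 | 11.2% | upward |
| 1 | 12.6% | none |
| 2 | 15.1% | downward |
| 5 | 21.5% | downward |

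The k = 0 row equals the competing-event value, 0.005/0.028 × (1 − 0.972^28) = 9.8%. It is also the right answer if only transfusions in the study NICU count.

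**Step 5: end of the study period.** Censoring at the close of the six-week window is set by the calendar, not by the infant's condition. It is a legitimate use of censoring and is not part of this point.

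**The case against.** The strongest defence is that the third sentence uses the word loosely, meaning only that the clock stops when an infant leaves, and that the first sentence governs. That may be the intention. However, the word has a fixed and different meaning in the named software, and the sentence puts transfer and discharge together under it. If the loose meaning was intended, transfer is left with no status at all. The wording needs correcting on either reading.

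A second defence is proportion. The study is observational, section 5.3 attaches no hypothesis test to this outcome, and the difference may be small if most transfusions precede most discharges. This stands as a limit on the consequence. It does not remove the contradiction.

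Three stronger readings are tempting, and the SAP does not support them:

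- **Censoring transfers also biases the result upward.** Transfer is only ever censored, and step 4 shows that the direction can go either way. The SAP does not say that infants leave because they are stable. Section 4.4 counts the centers that perform NEC surgery, so some may not, and transfer of sicker infants is plausible.
- **The true overstatement is larger because leavers are at lower risk than stayers.** The competing-event value already counts no transfusions after departure. Any that do occur raise the true any-hospital risk and narrow the gap.
- **The bias distorts comparisons between countries.** Section 5.3 specifies no country breakdown for this outcome; country-level reporting is set out for the prevalence rates in sections 5.1 and 5.2.

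**Conclusion.** The contradiction on discharge is real, is not resolved elsewhere in the SAP, and affects a main outcome that cannot be run as written. The upward direction under the censoring sentence is certain relative to the SAP's own competing-event definition, because it follows from the formula and not from the assumed rates. The size is not determinable from the SAP. Under the assumed ranges it is about 1% relative at the low end and 40% or more where about half or more of the infants are discharged by day 28 under flat hazards. With early transfusion and late discharge it stays below 15% even when 60% are discharged. For transfer there is no contradiction and no established direction of bias. What is missing is a stated target against which the censoring rule could be judged.

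**What to change.** Remove discharge from the censoring sentence in section 5.3 and list one status per infant, by whichever comes first: 1 = first platelet transfusion, 2 = death, 3 = discharge alive, 0 = end of the study period or day 28.

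Then state the target and let it decide the transfer code:

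- **Transfusion in the study NICU:** transfer is also a competing event, with its own code.
- **Transfusion in any hospital:** transfer may stay censored, with an explicit statement that this assumes non-informative transfer.

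Report the other transfer coding as a sensitivity analysis.

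The cost is a few lines of SAP text, one recoded status variable and one additional run. It does not require splitting transfers by destination; the SAP does not show that destination was recorded, so a rule built on it might need data that are not available.
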